12.2 Analytical population

12.2.1 Full analysis set

The primary outcome will be comparatively analyzed based on “modified intention-to-treat (mITT)”. In the mITT analysis, patients will be analyzed according to their randomization allocations. If patients randomly assigned to the IA group actually receive EA during surgery, they will be analyzed according to the IA group in mITT analysis. If patients randomly assigned to group EA actually receive IA during surgery, they will be analyzed according to group EA. Patients who meet the exit criteria after randomization will not be included in the mITT population.

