5.3 Exit criteria

- (1) Patients with other non-tumor diseases that prevent them from continuing to receive this treatment regimen.
- (2) Patients who need emergency surgical resection due to intestinal obstruction, intestinal perforation, intestinal bleeding, etc. after being enrolled in the study.
- (3) Patients with distant metastasis confirmed by intraoperative exploration or postoperative pathology, including liver, pelvic cavity, ovary, peritoneum, distant lymph node metastasis, etc.
- (4) Patients who need combined organ resection as determined by intraoperative exploration.

(5) Patients who request to withdraw from this study cohort for various reasons after being enrolled in the study, or who cannot complete the study plan and follow-up for various reasons.

The data of patients who withdrew from the study were not used, and these patients were not allowed to re-enter the study.

6. Study treatment grouping

Experiment group: Total laparoscopic intracorporeal anastomosis group (IA group)

The tumor is resected according to surgical specifications for radical colon cancer surgery. Mesentery resection is performed under laparoscopy, and anastomosis is completed under laparoscopy. A small incision is made to extract the specimen after the anastomosis is completed.

Control group: Laparoscopy assisted extracorporeal anastomosis group (EA group)

The tumor is resected according to surgical specifications for radical colon cancer surgery. A small incision is made in the middle of the abdomen to trim the mesentery, remove the specimen, and complete the anastomosis. After completing the anastomosis, the incision will be sutured.

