6.2 Blinding and unblinding

The clinical surgeons, outcome assessors, data recorders, and statisticians will all operate independently. Due to the nature of the surgical interventions, the surgeons will not be blinded to treatment allocation. However, the outcomes assessor who assess or analyze the end point will be blinded. The patients will also be blinded to group allocation to reduce the risk of bias. Unblinding will not be performed unless the finalization of the main data analysis or required for patient's safety. After the data analysis, we will have a blinded interpretation of the study results to minimize misleading data interpretation.

7. Intervention and study flow

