7.4 Patients compliance and exit

To improve patient compliance, before randomization, physicians will communicate with patients in detail about surgical procedures, possible random groupings, relevant and evolving treatment, and patient safety and security conditions. They will obtain informed consent to ensure patients clearly understand the treatment and research procedures. The randomization time should be as close as possible to the time before surgery (the day before surgery) to prevent accidental exclusion of patients after randomization. After randomization, patients can withdraw from the trial at any time. If a patient requests withdrawal from the study, the main researcher at their research center will communicate with them to avoid disrupting the balance of random groups due to exclusion. If the patient still insists on withdrawing, they will be removed from the trial. Clinical information relating to this patient will not be included in any data analysis related to this trial.

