4.2 Analysis populations

4.2.1 Modified intention-to-treat (mITT) population

In the mITT analysis, patients will be analyzed based on their randomization allocations. If patients randomly assigned to the IA group receive EA during surgery, they will be analyzed within the IA group in the mITT analysis. If patients randomly assigned to group EA receive IA during surgery, they will be analyzed according to group EA. Patients who meet the exit criteria after randomization won't be included in the mITT population.

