4.3 Analysis of endpoints

The analyses of primary endpoint and secondary endpoints will be conducted in mITT population, PP population and AT population.

Analyses for the primary outcome variable will be unadjusted. In analyzing the primary outcomes, the rate of overall SSI will be reported as frequencies and percentages. We will calculate the absolute risk differences and the corresponding 95% confidence interval (CI) between two groups. If the absolute risk differences and the corresponding 95% CI are within the non-inferiority margin (<5%), non-inferiority is established. If not, IA is not non-inferior to EA.

The independent risk factor of the primary endpoint will be analyzed in the AT population. High-risk variables identified through univariable analysis and clinical experience will be included in the multivariable analysis. Multivariable logistic regression will be employed to identify independent risk factors for SSI. The effect size will be estimated using odds ratios (ORs) with 95% confidence intervals.

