4.5 Primary endpoint

The primary endpoint in this trial is surgical site infection (SSI) within 30 postoperative days. Cases that fail to complete the 30-day follow-up are treated as missing data. The SSI will be compared between groups in the mITT population, PP population, and AT population.

- Overall SSI, Categorical variable. The absolute risk differences and the corresponding 95% CI between two groups will be calculated. The 95% CI will be compared with the non-inferiority margin (5%).

The subtypes of SSI (Superficial or deep incisional SSI, and Organ/space SSI) will also be compared between the two groups. However, their 95% confidence interval will not be compared with the non-inferiority margin.

The independent risk factors for overall surgical site infection (SSI) will be analyzed in the AT population. In univariable analysis, continuous variables will be converted to categorical variables. Chi-square tests or Fisher's exact tests will be employed. The key variables are as follows.

- Sex (male, female);
- Age (≤ 65 years, > 65 years);
- Body Mass Index ($\leq 24 \text{kg/m}^2$, $> 24 \text{kg/m}^2$);
- American Society of Anesthesiologists grading (I, II, III);
- Eastern Cooperative Oncology Group performance status score (0, 1, 2);
- Tumor site (distal transverse colon, splenic flexure of colon, descending colon, and proximal sigmoid colon);
- NRS2002 score (≤ 2 points, > 2 points);
- Parenteral prophylactic antibiotics (Yes, No);
- Mechanical bowel preparation (No, only enema, only oral laxative, enema plus oral laxative);
- Oral antibiotic bowel preparation (Yes, No);
- Postoperative antibiotic use time (≥ 3 days, < 3 days);

- Pathological TNM stage (0, I, II, III);
- Overflow of intestinal contents during anastomosis (Yes, No);
- Operating time (≤ 180 mins, > 180 mins);
- Blood loss during operation (≤ 100 ml, > 100 ml);
- Blood transfusion during operation (Yes, No);
- Prophylactic enterostomy (Yes, No);
- Anastomosis methods (Side-to-side anastomosis, End-to-side anastomosis, End-to-end anastomosis)
- Intervention (intracorporeal anastomosis, extracorporeal anastomosis)

Factors clinically relevant to SSI after univariable analysis will be included in multivariable analysis. Logistic regression will be used in multivariable analysis to identify independent risk factors for SSI. The effect size will be estimated using odds ratios (ORs) with 95% confidence intervals.

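### The mITT set drops any randomised patient who meets open-ended exit criterion (5), and an SSI recorded before withdrawal is barred from every analysis

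*Combined protocol and SAP*

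**What the plan says.** The primary analysis set is defined in Protocol v2.1, section 12.2.1: "Patients who meet the exit criteria after randomization will not be included in the mITT population". SAP 4.2.1 repeats the rule for "Patients who meet the exit criteria after randomization".

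Exit criterion (5) in Protocol 5.3 takes in patients who ask to withdraw, "or who cannot complete the study plan and follow-up for various reasons". It sets no end date and makes no reference to whether the SSI outcome is already known. The amendments summary lists it as an addition in version 2.0.

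Two further sentences deal with the data themselves. Protocol 5.3 says "The data of patients who withdrew from the study were not used". Protocol 7.4, on a patient who insists on withdrawing, says "Clinical information relating to this patient will not be included in any data analysis related to this trial".

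The SAP names three analysis sets: "The analyses of primary endpoint and secondary endpoints will be conducted in mITT population, PP population and AT population". For the primary endpoint, SAP 4.5 says "Cases that fail to complete the 30-day follow-up are treated as missing data". SAP 5 treats a missing primary outcome as censored and does not impute it. SAP 4.6 censors patients lost to follow-up for DFS and OS.

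**The concern.** Withdrawal or loss can follow a complication, and the complication of interest here is the primary endpoint. SSI is checked daily in hospital and weekly after discharge (Protocol 7.3), so an infection may well be on record before a patient leaves the trial. If that patient withdraws, the plan discards a known primary outcome. Exclusion after randomisation can then depend on the outcome, inside the set used for the non-inferiority test.

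The same patient is also given two dispositions. Under the mITT definition, someone who cannot complete follow-up is out of the set; under SAP 4.5, 4.6 and 5 that person is in the set as missing or censored. Nothing says which rule governs. No analysis of all randomised patients is planned, so a reader could not tell whether the conclusion depends on the exclusions.

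**Working it through.** **1. The plan's own sample size.** Inputs from Protocol 12.1: SSI 8.0% (IA) and 13.3% (EA), margin 5 points, one-sided 0.025, power 0.80, drop-out 20%.

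n per arm = (1.960 + 0.842)² × (0.080 × 0.920 + 0.133 × 0.867) / (0.05 + 0.053)² = 7.849 × 0.1889 / 0.010609 = 139.8, so 140. Then 140 / 0.80 = 175 per arm, 350 in total. This matches. So 175 per arm is the number before loss and 140 the number after it; the planned loss is 35 per arm.

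**2. What happens to an SSI that was seen before the patient left.**

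| Patient | mITT | PP and AT |
|---|---|---|
| Formally withdrew | Removed by exit (5) | Barred by Protocol 5.3 and 7.4 |
| Lost without withdrawing | Removed by exit (5) | Definitions carry no exit rule; depends on how SAP 4.5 is read |

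Read literally, SAP 4.5 could turn an SSI already seen into a missing value when the 30-day follow-up is incomplete. It can also be read as meaning only that the outcome is unknown.

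**3. Where the two SAP rules differ in effect.** For SSI, an unimputed missing outcome leaves the risk-difference denominator, just as an excluded patient does. Only the reported set size and the disclosure differ. For DFS and OS, a patient lost in year 3 contributes three years at risk if censored and nothing if excluded, so the results differ.

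**4. False non-inferiority (assumed exits).** True rates are placed at the margin: EA 13.3%, IA 13.3 + 5 = 18.3%. There are 175 per arm before exclusion. Infected patients are removed, and non-inferiority is declared when the upper Wald 95% limit is below 5 points. Results are by binomial simulation.

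| Infected patients removed | False non-inferiority |
|---|---|
| None | 2.6% |
| 3 IA | 6.4% |
| 3 IA, 2 EA | 3.9% |
| 3 IA, 3 EA | 3.2% |
| 3 EA | 1.1% |

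**5. Even-handed exits.** If every infected patient has the same chance w of exit in both arms, the rate seen is p(1 − w)/(1 − pw).
- At the margin, w = 10% removes about 0.1 × 175 × 0.183 = 3.2 IA and 0.1 × 175 × 0.133 = 2.3 EA patients. The difference falls from 5.0 to 4.65 points, and false non-inferiority is 3.3%.
- At w = 20% the difference is 4.27 points and false non-inferiority is 4.2%.
- At the design rates, w = 10% moves the difference from −5.3 to −4.9 points, against IA.

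**6. Tipping point.** Start from the design rates after the planned loss, about 11/140 IA v 19/140 EA. Upper limit = difference + 1.96 × √[pI(1 − pI)/nI + pE(1 − pE)/nE].

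| Restored | Counts | Upper limit (points) | Non-inferior |
|---|---|---|---|
| Nobody | 11/140 v 19/140 | +1.5 | Yes |
| 5 infected IA, nobody else | 16/145 v 19/140 | +5.1 | No |
| 5 infected IA and 1 infected EA | 16/145 v 20/141 | +4.5 | Yes |
| 5 infected IA, plus 10 uninfected per arm | 16/155 v 19/150 | +4.8 | Yes |
| 5 infected IA, rest uninfected, to 175 per arm | 16/175 v 19/175 | +4.6 | Yes |

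With all 35 per arm restored, the conclusion reverses at 6 infected IA patients if no restored EA patient was infected (17/175 v 19/175, +5.2). If 5 restored EA patients were infected, it takes 10 (21/175 v 24/175, +5.3).

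**The case against.** The best defence is that nothing in the documents points to lopsided exits. Patients are blinded (Protocol 6.2), randomisation is placed close to surgery (7.4), retention is actively managed (7.3), and missing data will be stated in the tables (SAP 5). With even-handed exits the effect is small, and at the design rates it runs against IA. This stands as to likely size. None of these measures brings back an SSI that the plan discards.

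Second, the PP and AT definitions do not contain the exit rule, and SAP 4.5 can be read as covering unknown outcomes only. This also stands. A reader might infer that every lost patient's SSI vanishes from every analysis; the documents establish that only for patients who formally withdraw.

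Third, the conflict with the SAP's missing-data rules does not change an unimputed SSI risk difference. A reader might infer that it alters the primary estimate; it does not. For DFS and OS it could be argued that the more specific censoring rule governs, but the plan does not say so.

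Fourth, withdrawal has to be respected. The bar on withdrawn patients' data was already in version 1.0, and the consent form is not among the material available here, so whether patients already withdrawn agreed to retention of earlier data cannot be checked. That limits what can be recovered for them.

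**Conclusion.** The point holds. As written, the primary set excludes randomised patients on an open-ended criterion that can depend on the outcome, and a withdrawn patient's recorded SSI is lost to all three planned sets. For patients lost without withdrawing, removal is explicit for mITT only, and SAP 4.5 needs clarifying. The conflict between exclusion and censoring matters for the results of DFS and OS, which are secondary.

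A reader might go further and conclude that the primary result is biased towards non-inferiority. The documents do not support that: they give no exit counts, and the direction depends on which arm loses infected patients (6.4% with three from IA only, 1.1% with three from EA only, against 2.6%). Nor do five lost IA infections in themselves overturn a result at the design rates. They do so only in the worst case, where nobody else is restored.

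All scenario figures rest on assumed exits, the Wald interval and the design or margin rates. On those terms the effect is small unless exits are lopsided. It should still be fixed, because no planned analysis would show whether they were.

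**What to change.** - In Protocol 12.2.1 and SAP 4.2.1, stop using exit (5) to remove patients from mITT. Treat loss to follow-up as missing for SSI and censored for DFS and OS, and reconcile exit (5) with SAP 4.5, 4.6 and 5.
- Amend Protocol 5.3 and 7.4, and clarify SAP 4.5, so that data collected up to withdrawal or loss are used where consent allows, and an SSI observed before then counts as an event.
- Report post-randomisation exclusions by arm and reason.
- Add a sensitivity analysis of SSI in all randomised patients with outcome data, with a tipping-point analysis for missing outcomes.

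The cost is wording in both documents and one sensitivity table. N = 350 and the trial procedures are unchanged. The downside is that some retained patients will have incomplete outcomes that must be handled, and use of data from patients already withdrawn depends on the consent they gave.

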12.2.2 Per-protocol analysis

In per-protocol (PP) analysis, only cases treated strictly in accordance with random groups and assigned treatment plans will be included. Patients who haven't been treated with a randomly assigned protocol will be excluded from the per-protocol analysis.

12.2.3 As-treated analysis set

In the as-treated (AT) analysis set, we'll analyze patients according to the actual treatment they received instead of the allocated plan for random groups.

12.3 Effect analysis and statistical method

12.3.1 primary endpoint analysis

In analyzing the primary outcomes, the rate of overall SSI will be reported as frequencies and percentages. We will calculate the absolute risk differences and the corresponding 95% confidence interval (CI) between two groups. If the absolute risk differences and the corresponding 95% CI are within the non-inferiority margin (<5%), non-inferiority is established. If not, IA is not non-inferior to EA. The analysis of the primary endpoint will be carried out in the mITT population, the PP population, and the AT population.

The independent risk factor of the primary endpoint will be analyzed in the AT population. High-risk variables identified through univariable analysis and clinical experience will be included in the multivariable analysis. Multivariable logistic regression will be employed to identify independent risk factors for SSI. The effect size will be estimated using odds ratios (ORs) with 95% confidence intervals.

12.3.2 Secondary endpoint analysis

The analysis of the secondary endpoints will be carried out in the mITT population. In the analysis of secondary endpoints, categorical variables will be reported as frequencies and percentages. Groups will be compared using the χ^2 test or Fisher's exact test. Absolute risk differences and the corresponding 95% CI will be calculated. Continuous variables will be described as mean \pm standard deviation or median (quartile). Groups will be compared using the t-test or Mann-Whitney U test, as appropriate. Hodges-Lehmann method will be used to calculate the difference in median and the corresponding 95% CI.

The comparison of 3-year DFS and 3-year OS between the two groups will utilize the Kaplan-Meier curve and the Cox proportional risk model. Relevant risk factors will be adjusted in Cox proportional risk model.

The missing data in this trial is expected to be minimal. If it occurs, it will be treated as censored data and not imputed. All statistical tests were 2-sided, and statistical significance was set at $P < 0.05$. All statistical analyses were performed using R or SPSS.

12.4 Interim analysis

There will be no interim analysis for this study

12.5 Terminal analysis

We will conduct an analysis of the main endpoints of the study and publish the relevant findings after all patients have completed the first month of follow-up after surgery. After all patients have completed 5 years of follow-up, we will analyze results involving survival data, and publish relevant research results.

12.6 Data Monitoring Committee

The data and safety monitoring board (DSMB) was composed of senior surgeons, ethicists, and statistical analysts. Each member of the DSMB is independent of this trial and is not likely

to affect the competitive interests of the trial. The DSMB will receive and review the safety data for this trial. If the DSMB believes the number of adverse events in the trial is biased between groups, they will notify the chair of the trial steering committee.

There will be no interim analysis for this project. However, once the study begins, the DSMB will evaluate the results of the study every year. The assessment included primary and secondary endpoint records, adverse events, and loss of study samples. It also assesses differences with expectations, and potential conflicts with new findings and/or developments in the field of colon cancer. DSMB members are not allowed to share confidential information with anyone outside of the DSMB, with the exception of the trial steering committee.

The techniques used in this research institute are all techniques currently used in surgical treatment of colon cancer, and patients are not at higher risk. Therefore, this study did not set suspension parameters for the entire project. However, if in the DSMB's regular assessments, a center shows a huge difference in safety indicators compared to other centers and is significantly worse than the current international level, then the DSMB will submit its recommendations in writing to the trial steering committee, requesting that the trial plan be revised, or the quality of cases in the corresponding center be re-evaluated, or even suspended or terminated the clinical trial enrollment of the corresponding center.

At the discretion of the DSMB during the trial process, the DSMB may decide to meet early to discuss testing procedures together about adverse events and promptly clarify any issues with key investigators.

13. Data collection and management

13.1 Electronic Case Report Form

An electronic case report form (eCRF) is developed by the lead investigator. The CRF table includes the primary endpoint and Secondary endpoints. Additionally, general baseline data on patients will be included.

All relevant clinical data including demographic and medical information will be collected from the electronic medical record. The collected data will be encoded to protect the privacy of all participants and then be entered into an eCRF by trained research assistants in each sub-

center. Double data entry will be performed to ensure that the data collected are accurate and verifiable from source documents. Input rules including field and range checks will also be set to minimize data entry errors. The research coordinator will periodically check the data distribution, verify outliers, and track missing data to improve data integrity and data validation.

13.2 Data management

Data storage and backup will be managed by the edocdata platform (<https://jlcrc.edocdata.com/>), which will track all changes to the data and retains a history for each variable. Unauthorized persons or institutions will not be able to access any data stored on this server. When the trial is completed, the data will be locked and stored on edocdata platform, after which the researchers can no longer modify the data. Both paper and electronic documents will be preserved for at least 5 years after publication.

14. Ethics

14.1 Ethics Committee

This trial has been approved by the Ethics Review Committee of the First Hospital of Jilin University (Approval number: 19K135-001). Each sub-center must conduct an ethical application before participating in this trial.

14.2 Patients information and informed consent

Eligible patients should receive in-person notification from the treating surgeon and written information about the trial. Each patient should provide informed consent in accordance with local ethics committee guidelines before entering the random allocation of studies.

The informed consent procedure should be carried out by the doctors of each centre. Information provided to patients with informed consent includes: 1) a statement about the study involved in the trial; 2) a full and fair explanation of the procedures to be followed; 3) a full explanation of the nature, anticipated length, and purpose of the study; 4) a description of any risk or discomfort that the patient can reasonably anticipate; 5) a description of any benefits that can be reasonably anticipated; 6) a statement that patient data will be treated with care and confidentiality and that the data will be kept for 15 years; 7) a statement about the patient's physical material will be kept for 15 years; 8) a statement about voluntary participation, where

the statement will state the refusal Participation in the trial does not involve any punishment or loss of benefits the patient is entitled to, and patients can stop participating at any time without being penalized or losing benefits, in which case the patient will receive standard treatment with the same level of care.

15. Definition of Study Completion

The completion of the study was defined as all enrolled patients completed 5 years of follow-up. Follow-up outcomes include disease-free survival, recurrence survival, death, or loss of visits.

16. Study organizational structure

